4. INTERVENTIONS

1 baseline and up to 4 further colposcopic examinations during the course of the year. This is 1-2 additional follow-up examinations in comparison to the normal 6 monthly follow-up appointments for patients that are currently having conservative management for CIN2

5. STATISITICS

6.1 The Number of Participants

We have identified 10 patients as a suitable number for this study (as it is a pilot). This will enable a robust analysis of the merits of non-invasive sampling and CIN2 progression. There is a risk of patients dropping out/ withdrawing consent during the study time period. Thus, we will only count patients that have completed the full study duration.

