1. SYNOPSIS

Study Title	Monitoring of Cervical lesions at Colposcopy using a novel non-invasive technique for monitoring of CIN2 lesions (a pilot/ feasibility study)			
Internal ref. no.	R&D			
Study Design	The is a single-centre, non-randomised, cohort interventional & lab based study			
Study Participants	Women with abnormal cytology attending the colposcopy clinic that have single quadrant disease that is histologically CIN2. The women will be identified from the larger Cervical Cell Lift study (17/SC/0203) or from the pre-existing standard of care conservative management pathway.			
Planned Sample Size	10			
Follow-up duration	From 6 months to 1 year (3 monthly intervals)			
Planned Study Period	12 to 18 months			
Primary Objective	To non-invasively monitor women with CIN2 using a novel non-invasive approach in order to identify biomarker patterns that are consistent with lesion regression/ progression			
Secondary Objectives	None			
Primary Endpoint	As this is a feasibility study, the outcome is considered to be the ability to identify biomarker patterns consistent with lesion regression/ progression			
Secondary Endpoints	-			
Intervention (s)	 If enrolled to the study after CIN2 diagnosis: Primary visit for Colposcopy – CIN2 identified, acetowhite photograph and Patch taken followed by biopsy 3-month visit for Colposcopy – Patch, acetowhite photograph taken and colposcopy done to ensure no change in lesion and comparison with previous photograph of acetowhite change 6-month visit for Colposcopy - Patch, acetowhite photograph taken and colposcopy done to ensure no change in lesion and comparison with previous photograph of acetowhite change 9-month visit for Colposcopy - Patch, acetowhite photograph taken and colposcopy done to ensure no change in lesion and comparison with previous photograph of acetowhite change 9-month visit for Colposcopy - Patch, acetowhite photograph taken and colposcopy done to ensure no change in lesion and comparison with previous photograph of acetowhite change 1-year visit for Colposcopy – Patch, acetowhite photograph taken and either further biopsy or excisional treatment as per colposcopist impression If enrolled to the study from the pre-existing clinical pathway, participants will start the study at either the 3 month visit (-/+ 2 week) or the 6 month routine clinical visit (-/+ 2 week) following CIN2 diagnosis. 			

BACKGROUND AND RATIONALE

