Outline the scientific justification for the research. Give an outline of the background to the study, with references to literature and other relevant research.

Give an outline of the main research questions. Give a brief outline of the intervention (if applicable) and summary of findings from previous studies (if relevant) that potentially have clinical significance.

Provide summary of the known and potential risks and benefits of any of the study procedures (where applicable)

Describe the population to be studied.

The purpose of this study is to non-invasively monitor women with histologically identified CIN2 lesions. CIN2 lesions are pre-cancer lesions that are caused by HPV. These lesions can in a small subset of patients progress onto CIN3 lesions and eventually cervical cancer. The duration of this progression is usually over 1 year (for CIN3 and longer for cervical cancer) and indeed the majority of these lesions would actually regress (especially in <30 year olds) due to immune control and HPV clearance(1–5). This understanding of CIN2 progression has led to changes in the management of CIN2 lesions, where in the past all such patients would be offered excisional treatment, we have now moved towards adopting a watch and wait policy (with usually 6 monthly colposcopy follow-ups)(6).

Our current ongoing study (17/SC/0203 - Collection of Cervical Cells at Colposcopy using a novel technique for analysis of high risk vs. low risk lesions) has demonstrated that using our non-invasive approach we can identify high-grade (CIN2+) and low-grade (CIN1/ negative) lesions using a biomarker panel. This approach has yielded numerous advantages and in particular the ability to identify lesions in their entirety together with their location on the cervix (Fig 1). This approach is now being validated on a larger cohort of patients and is being assessed to become the test of choice for HPV triage. The biomarkers we have settled on are p16/MCM (markers of CIN2+) and E4 (marker of CIN1). These markers have been independently verified by our group and others as being sensitive markers to clinically relevant disease and indeed this panel of markers, by improving the objectiveness of diagnosis, improves the sensitivity of subjective approaches such as histology/ cytology to CIN2+ lesions(7).

Fig 1. Patch stained with MCM demonstrating a CIN3 lesion in its entirety. Inset demonstrates lesion magnified

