The study will involve monitoring patients with our non-invasive technique in conjunction with colposcopy (Fig 3) to assess the feasibility of this method. The main risk to any patient is the risk of progression to CIN3 and worse cancer. However, as the majority of CIN2 patients across the UK are now offered conservative management and as many recent papers have demonstrated lesion regression in >50% of CIN2 cases this risk (over the duration of the study) is extremely low(1–6). Moreover, in order to further minimize this risk, we will follow-up these patients more intensively than the norm (usually conservative management of CIN2 involves 6-month follow-up colposcopy) with 3 monthly colposcopy visits for up to 1 year with the same named colposcopist (to reduce any inter-observer variability) where possible. If a different colposcopist is used, we will aim to mitigate

any increased variability by using and comparing colposcopic photographs taken during each colposcopy visit. This will allow us to ensure that variations in diagnosis are kept to a minimum.

Finally, as we are using biomarkers to identify lesions on the patch, any marker pattern that is suggestive of higher-grade disease will result in the patient having a colposcopic visit together with adequate counselling and biopsies/ treatment as required. We feel that this approach enables us to minimize the already low risk of progression even further thus allowing women to give informed consent in an ethical manner. There are no operceivable risks involved.

Fig 3. Study scheme demonstrating entire patient pathway including patient withdrawal points. Colposcopic photographs will be taken during each colposcopy visit and all histology will be reviewed/compared by histopathologists. A) Pathway for patients who recruited after diagnosis with CIN2, B)) Pathway for patients who recruited from the pre-existing clinical pathway either at 3 month visit (-/+ 2 week) or at the 6 month routine clinical visit (-/+ 2 week).

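### Section 6.1 claims a robust analysis of CIN2 progression from 10 women, but by the protocol's own account few or none of them will progress

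*Protocol*

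**What the plan says.** Section 6.1 of the Protocol gives one reason for the sample size: "We have identified 10 patients as a suitable number for this study (as it is a pilot"). The next sentence states what that number will deliver: "This will enable a robust analysis of the merits of non-invasive sampling and CIN2 progression".

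The Background and Rationale describes how often and how fast these lesions progress. On frequency: "These lesions can in a small subset of patients progress onto CIN3 lesions and eventually cervical cancer". On timing: "The duration of this progression is usually over 1 year (for CIN3 and longer for cervical cancer"). On progression as the main risk to participants: "this risk (over the duration of the study) is extremely low". On the opposite outcome, it cites "lesion regression in >50% of CIN2 cases".

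The Synopsis gives the follow-up as "From 6 months to 1 year (3 monthly intervals"). Women who join from the existing clinical pathway start at their 3- or 6-month visit after diagnosis, so many may be observed for less than a year.

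The Synopsis and sections 3.1 and 4.2 all name marker patterns for both regression and progression. Section 6.2 plans to correlate marker patterns with the final histology or colposcopy outcome. Section 4.5 allows the final number to exceed 10, and also stops data capture at the end of 2022 even if 10 evaluable women have not been reached.

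**The concern.** The protocol uses the rarity of progression to reassure on safety, and then claims that the same 10 women allow a robust analysis of progression. An analysis of which marker patterns go with progression needs women who progress. If progression is as uncommon as the Background says, and usually takes longer than the follow-up, there may be none, or only one or two.

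Two things are at stake. The first is how the results are read: section 6.1 invites a reader to give weight to a progression pattern seen in one woman, or to the lack of one. The second is the justification of the study. The Ethics section defends the extra visits partly by what the work could show about marker patterns for regression and progression, and says it could inform who is offered conservative or excisional treatment. What 10 women can contribute on progression should be stated accurately.

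**Working it through.** **Inputs from the Protocol**
- Planned number n = 10 (Synopsis; section 6.1).
- Basis for n: that the study is a pilot. No progression rate, precision or expected count is given, so there is no sample size calculation to reproduce.
- Progression: a small subset, usually slower than one year, extremely low risk over the study (Background and Rationale). These statements are qualitative.
- Maximum follow-up: one year (Synopsis).

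**Assumed input.** The progression rate p during follow-up is not in the document. I take 5, 10, 15 and 20%. The protocol's wording points to the lower end.

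**Formulas**, treating women as independent with a common rate:
- expected progressors = n × p
- chance of no progressor = (1 − p)^n
- chance of at least three = 1 − the sum over k = 0, 1, 2 of C(n,k) p^k (1 − p)^(n−k)

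**Results for n = 10**

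| Assumed p | Expected progressors | Chance of none | Chance of at least one | Chance of at least three |
|---|---|---|---|---|
| 5% | 0.5 | 0.95^10 = 60% | 40% | 1% |
| 10% | 1.0 | 0.90^10 = 35% | 65% | 7% |
| 15% | 1.5 | 0.85^10 = 20% | 80% | 18% |
| 20% | 2.0 | 0.80^10 = 11% | 89% | 32% |

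Below this range the position is worse: at 2% the expected number is 0.2 and the chance of none is 82%. Above it, at 25%, the expected number is still only 2.5.

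**If the final number is not 10** (section 4.5; 8 and 15 are illustrations)

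| Assumed p | n = 8: expected | n = 8: none | n = 15: expected | n = 15: none |
|---|---|---|---|---|
| 5% | 0.4 | 0.95^8 = 66% | 0.75 | 0.95^15 = 46% |
| 10% | 0.8 | 0.90^8 = 43% | 1.5 | 0.90^15 = 21% |
| 15% | 1.2 | 0.85^8 = 27% | 2.25 | 0.85^15 = 9% |
| 20% | 1.6 | 0.80^8 = 17% | 3.0 | 0.80^15 = 4% |

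Even the most favourable cell, 15 women at 20%, yields about three progressors.

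**What the regression figure offers.** The protocol cites regression above 50%. With regression rate r, the expected number of non-regressors among 10 is 10 × (1 − r): 5 at r = 50%, 3 at an assumed 70%, and 1 at an assumed 90%. Non-regressors include every progressor, so this group can never be smaller than the group of progressors. It is not guaranteed to be large, because 50% is a lower bound for regression.

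**The case against.** The strongest reply is that this is openly a feasibility pilot. Section 6.1 justifies 10 on that ground, section 4.2 asks only for initial utility, and no test, success threshold or decision rule rests on the word robust. The sentence also covers the merits of non-invasive sampling, which 10 women can inform. All of this stands, and it is why the number itself is not criticised. It does not rescue the sentence as applied to progression, because nothing else in the protocol qualifies it.

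Secondly, the scarcity of progressors depends on a rate that the protocol does not give. This is also true. A reader might infer that no woman will progress, or that the progression part of the objective is bound to fail. The documents do not support that: at an assumed 10 to 20%, at least one progressor is more likely than not (65 to 89%). What holds across the range is weaker but sufficient: one or two progressors are too few for a robust analysis.

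Thirdly, section 4.2 speaks of regression or progression, so the endpoint is not shown to require progressors. Section 6.2 could be met by describing regressors against the rest. This is fair, and the fix builds on it.

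Finally, one might try to show the weakness with significance tests or with intervals for overall agreement. The protocol names neither, and section 6.2 speaks only of correlation using serial samples. Such figures would judge an analysis that is not planned, so the point does not rely on them.

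**Conclusion.** The concern holds as a fault in the claim, not in the sample size. Section 6.1 gives the design a property that the Background and Rationale contradicts. At assumed progression rates of 5 to 20%, 10 women yield 0.5 to 2.0 expected progressors, with a chance of none between 60% and 11%. At no rate in this range, and with no plausible drift of the final number around 10, is an analysis of progression robust.

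The calculation assumes independent women, a common rate, and a range for that rate which is mine and not the protocol's.

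A reader might infer that section 6.1 licenses a firm conclusion about progression, or that the study needs more women. The first goes beyond the text: the claim is loose and triggers no decision. The second does not follow, because 10 is acceptable for feasibility and description. The sentence should be corrected before results are reported.

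**What to change.** **Section 6.1.** Replace the sentence on robust analysis with wording to this effect: *Ten women will give descriptive, hypothesis-generating information on the feasibility of sampling and on marker patterns. Few or no progressions are expected, and no conclusion on progression patterns will be drawn from them.*

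**Section 6.2.** Make regression against non-regression (persistence or progression) the main descriptive contrast. Describe any woman whose lesion progresses individually.

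**Synopsis, sections 3.1 and 4.2.** Align the wording of the objective and endpoint with this contrast, so that they no longer promise patterns for progression as such.

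**Cost.** No added women, visits or samples; the contrast uses outcomes that the study already collects. It is more than an edit of one sentence, since it changes the main contrast in section 6.2 and touches the endpoint wording. The stated claim becomes less favourable, the contrast no longer isolates progression, and it could itself be sparse if regression is well above 50%.

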4.5 Definition of End of Study

The recruitment of new participants will stop when 10 evaluable patients have been recruited to the study or by the end of 2022, whichever is sooner. Evaluability is determined by having at least 3 full datasets (3 different time points). The study will end when the last patient has completed her last follow-up visit. Any participants recruited after the 10th evaluable participant who are still active in the study will be followed -up and included in the final analysis. The total number of participants recruited to the study may therefore be more than 10. All data capture will stop at the end of 2022, regardless of whether the full set of 10 evaluable participants has been accrued.

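### Section 6.1 counts only women who complete the full study, which conflicts with the three-dataset rule in 4.5 and may drop women biopsied or treated early from the outcome correlation

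*Protocol*

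**What the plan says.** Protocol 6.1 sets the target without a calculation: "We have identified 10 patients as a suitable number for this study (as it is a pilot". It then notes that "There is a risk of patients dropping out/ withdrawing consent during the study time period" and concludes "Thus, we will only count patients that have completed the full study duration".

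Protocol 4.5 works to the same number by another rule: "Evaluability is determined by having at least 3 full datasets (3 different time points". Recruitment stops at ten such women or at the end of 2022. Women recruited after the tenth evaluable one "who are still active in the study will be followed -up and included in the final analysis". It adds: "All data capture will stop at the end of 2022, regardless of whether the full set of 10 evaluable participants has been accrued".

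Two other places bear on who completes. The Background and Rationale says "any marker pattern that is suggestive of higher-grade disease will result in the patient having a colposcopic visit", with counselling and biopsy or treatment if needed. The caption of the pathway figure there says that it marks withdrawal points; the figure itself is not shown.

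Protocol 6.2 relates the biomarker patterns to each woman's final outcome, which may come from histology or from colposcopy.

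**The concern.** Both rules say who makes up the ten, and they do not give the same answer. The protocol itself fixes both, so a statistical analysis plan could not follow the two together.

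The rule in 6.1 also carries a risk of bias. Its stated reason is dropout and withdrawn consent, but as worded it covers any reason for not finishing. A woman whose patch suggests higher-grade disease may be biopsied or treated before month 12. If that ends her schedule, she is not counted, and the cause is her marker pattern together with her disease course. Those are the two variables that 6.2 correlates. The objective covers regression and progression, and in a study of ten women the progression side may rest on one or two.

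**Working it through.** **1. Schedule.** The Synopsis and the Interventions section give a baseline visit and up to four more, at months 3, 6, 9 and 12. (The Synopsis lists month 9 twice; the total of four follow-up visits shows this to be a repeat.) Women from the clinical pathway enter at month 3 or month 6. I read full duration as reaching the month-12 visit, and assume one dataset per visit and no missed visits.

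**2. Both rules at every possible last visit.**

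| Entry | Last visit (month) | Datasets | Evaluable under 4.5 | Counted under 6.1 |
|---|---|---|---|---|
| Baseline | 0 | 1 | no | no |
| Baseline | 3 | 2 | no | no |
| Baseline | 6 | 3 | **yes** | **no** |
| Baseline | 9 | 4 | **yes** | **no** |
| Baseline | 12 | 5 | yes | yes |
| Month 3 | 3 | 1 | no | no |
| Month 3 | 6 | 2 | no | no |
| Month 3 | 9 | 3 | **yes** | **no** |
| Month 3 | 12 | 4 | yes | yes |
| Month 6 | 6 | 1 | no | no |
| Month 6 | 9 | 2 | no | no |
| Month 6 | 12 | 3 | yes | yes |

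The rules disagree at three exit points and coincide for month-6 entrants. The third dataset always falls 6 months after entry, whereas full duration takes 12, 9 or 6 months depending on the route.

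**3. Calendar.** This version is dated 21/01/2022 and data capture ends with 2022. A baseline entrant enrolled on the version date would be due her month-12 visit on about 21/01/2023, after capture has stopped. She could still reach three datasets by about July 2022. Women enrolled earlier are not affected.

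**4. Could early-treated women be lost?** The Background allows biopsy or treatment after a higher-grade pattern. Section 3.4 otherwise plans no further biopsy before the 12-month visit, so early biopsy or treatment departs from the planned course. No section says that such a woman still counts. The rule in 4.5 alone would not rescue all of them: a woman treated with one or two datasets fails it too.

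**5. Size, on assumed rates.** The documents give no progression rate and no sample-size inputs, so the figure of 10 cannot be reproduced. Let q be the share of women who progress and are treated before month 12. Then P(at least one in 10) = 1 − (1 − q)^10:

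- q = 5%: 1 − 0.95^10 = 0.40; expected number 0.5
- q = 10%: 1 − 0.90^10 = 0.65; expected number 1
- q = 20%: 1 − 0.80^10 = 0.89; expected number 2

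If none of them completes, none is counted under 6.1.

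If instead a share p progress and a fraction f of those leave early, while all others complete, progressors make up p(1 − f)/(1 − pf) of the counted women:

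- p = 0.15, f = 0.7: 0.045/0.895 = 5.0%
- p = 0.10, f = 0.9: 0.010/0.910 = 1.1%
- p = 0.20, f = 0.5: 0.100/0.900 = 11.1%

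These shares do not depend on how many women are recruited.

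**The case against.** The best defence is that 6.1 is only a replacement rule. It sits under the number of participants, follows from a remark on dropout, and does not say that data from uncounted women are left out of 6.2. Analysis sets are often left to a statistical analysis plan. This has force: 6.1 does not formally define an analysis set. But even as a tally, 6.1 and 4.5 count the same ten differently, and 6.1 names no other set for analysis.

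Full study duration is also undefined, and the Synopsis gives follow-up as 6 months to 1 year. If 6 months were enough for everyone, the two rules would agree on the schedule above. The more natural reading is that the range reflects the entry routes (6, 9 or 12 months). Under either reading, women who leave before their third dataset remain uncounted.

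The Background calls the risk of progression over the study very low, so the assumed rates may be too high. That stands; with a lower q the probabilities fall. Continued recruitment could also bring the count back to ten, but step 5 shows that it does not restore the share of progressors.

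A reader might go further in three ways that the documents do not support:

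- **That a woman who progresses can never be a completer.** No text says that a treated woman must leave, the withdrawal points cannot be seen, and progression found at the 12-month visit is found in a completer.
- **That a woman last seen at month 6 lacks the outcome 6.2 needs.** Colposcopy is accepted as an outcome, and every follow-up visit includes it.
- **That the rule makes retention 100% by construction and so spoils a feasibility result.** Retention is not a stated endpoint, and nothing prevents withdrawals from being reported.

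**Conclusion.** The conflict between 6.1 and 4.5 is explicit and should be resolved. It affects baseline entrants last seen at month 6 or 9 and month-3 entrants last seen at month 9, taking full duration to mean reaching the month-12 visit.

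The loss of women biopsied or treated early is a conditional risk. It holds if they do not complete the schedule and if 6.1 governs who enters 6.2. In that case the selection depends on both marker and outcome, and can leave no progressors to describe. The chance that at least one woman in ten is affected is 0.40 to 0.89 for assumed rates of 5% to 20%; no rate in the documents narrows this.

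**What to change.** - Delete the last sentence of 6.1.
- In 4.5, use the three-dataset rule only as the tally that stops recruitment. A woman with fewer than three datasets does not add to that tally but is still analysed.
- In 6.2, analyse every enrolled woman with histologically confirmed CIN2, at least one stained patch and a histology or colposcopy outcome. Where biopsy or treatment comes early, take the outcome at that point as final, with all patches taken before it.
- Report withdrawals over all enrolled women, and show completers as a sensitivity display.
- Flag each outcome whose biopsy was triggered by the marker. Such histology is obtained because of the marker, so its agreement with the marker needs cautious reading.

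The cost is wording in 4.5, 6.1 and 6.2. It needs no extra patients or procedures and changes no clinical rule. The downside is that trajectories will differ in length, and women with one or two patches will inform the outcome correlation but say little about marker change over time.
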